8.2. Null hypothesis

H0: No statistically significant differences are observed with respect to the clinical parameters CRC, at 12 months between the two treatment modalities (i.e., MCAF + CM or MCAT technique with CM).

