STATISTICAL CONSIDERATIONS	Hypothesis tested: no statistically significant differences are observed with respect to the clinical parameters CRC, at 12 months between the two treatment modalities (i.e., MCAF + CM or MCAT technique with CM). Sample size calculation: the needed number of patients to be enrolled in this study is 17 for the test group MCAF + Fibro-Gide and 17 for the MCAT + Fibro-Gide. However, the number of patients will be increased of 1 patient for each arm considering the possibility of dropout, so the required number will be 18 for each group. Primary method of analysis: the significance of the difference within each group and between groups before and after treatment will be evaluated with the paired samples t-test or two independent samples t-test, as appropriated, regarding all numerical data (REC, KTW, GT, PPD, percentage of root coverage and VAS scale). Fisher's exact test will be applied for categorical data (frequency of complete root coverage). Differences will be considered statistically significant when the p-value was <0.05.
DURATION OF STUDY PERIOD	Global: 2 years Per patient: 1 years

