8.3. Statistical Methods

Statistical analysis will be performed using commercially available software (STATA) or R environment (www.r-project.org). Both patient- and tooth-level analysis will be performed for each parameter. Therefore, mean values and standard deviations (SD), as well other descriptive statistics, for the clinical variables will be calculated for each patient per treatment.

A mixed model will be built to take into account the variability due to patient and tooth factors differentially.

Accordingly, the significance of the difference within each group and between groups before and after treatment will be evaluated with the paired samples t-test or two independent samples t-test, as appropriated, regarding all numerical data (REC, KTW, GT, PPD, percentage of root coverage and VAS scale).

Fisher's exact test will be applied for categorical data (frequency of complete root coverage).

P-values will be computed by means of permutation methods to avoid any distributional assumptions or asymptotical approximation. Differences will be considered statistically significant when the p-value was <0.05 .

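### The primary CRC comparison has a null hypothesis worded as a test result, no stated unit of analysis, and no effect estimate or interval

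*Combined protocol and SAP*

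**What the plan says.** The primary outcome in Section 4.1 is the percentage of CRC at 12 months. Section 8.2 states the null hypothesis as "No statistically significant differences are observed with respect to the clinical parameters CRC, at 12 months between the two treatment modalities", and the Synopsis repeats it: "Hypothesis tested: no statistically significant differences are observed with respect to the clinical parameters CRC".

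Section 8.3 contains these elements that could bear on CRC:

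- Test: Fisher's "exact test will be applied for categorical data (frequency of complete root coverage").
- Threshold: "Differences will be considered statistically significant when the p-value was <0.05".
- Level: "Both patient- and tooth-level analysis will be performed for each parameter".
- Model: "A mixed model will be built to take into account the variability due to patient and tooth factors differentially". No outcome, link or treatment estimate is given.
- Descriptive statistics: means and SDs, "as well other descriptive statistics, for the clinical variables will be calculated for each patient per treatment".
- P-values from permutation methods, with no statement of what is permuted.

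The t-tests do not cover CRC. They are planned "regarding all numerical data (REC, KTW, GT, PPD, percentage of root coverage and VAS scale").

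Section 6.1 requires at least two recessions per patient, and Section 5.1 assigns one treatment to each patient. The only numerical difference in Section 8.1 is 10%, given for mean root coverage with an SD of 10%. Sections 1 and 4 state the aim as a comparison with published results and, secondarily, as patients' preference between the techniques.

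**The concern.** Three things are left open for the primary result.

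1. **Hypothesis.** A null hypothesis should be a statement about population parameters that the data may or may not contradict. As worded, it is satisfied by any p≥0.05, whatever the observed gap.
2. **Estimate.** No CRC effect measure, confidence interval or equivalence margin is specified, and no rule says how a non-significant result is to be read.
3. **Unit.** Section 8.3 asks for patient- and tooth-level analysis of every parameter, and Fisher's test is the only method named for CRC. Nothing says which unit the primary test uses. Teeth in one mouth share a surgeon, a session and a patient, so they are not independent.

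The unit matters most. It decides what the primary endpoint is and whether the stated 0.05 level holds. The first two decide whether a reader can tell a trial that found little difference from one that could not tell.

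**Working it through.** **Plan's own figure.** For a difference of 10, SD 10, two-sided α 0.05 and power 80%, the noncentral-t power is 78.1% at 16 per arm and 80.7% at 17. The stated 17 per arm is reproduced as a comparison of mean root coverage. The 10% is therefore not a CRC difference and cannot serve as a CRC margin. The documents give no CRC rates.

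**Patient level, no assumed rates.** Take 15/17 against 9/17, so 24 successes in 34. The one-sided hypergeometric tail is

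[C(17,15)·C(17,9) + C(17,16)·C(17,8) + C(17,17)·C(17,7)] / C(34,24)
= (3,306,160 + 413,270 + 19,448) / 131,128,140 = 0.0285.

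With equal arms the distribution is symmetric, so the two-sided p is 2 × 0.0285 = 0.057. Enumerating all outcomes, a gap of 6 patients is the largest that can be non-significant: 15 v 9 of 17 (6/17 = 35 points, p=0.057) or 16 v 10 of 18 (6/18 = 33 points, p=0.060).

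**What an interval adds.** For 15/17 v 9/17 the Wilson limits are 0.657 to 0.967 and 0.310 to 0.738. The Newcombe limits for the difference are

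- lower: 0.353 − √[(0.882−0.657)² + (0.738−0.529)²] = 0.045
- upper: 0.353 + √[(0.967−0.882)² + (0.529−0.310)²] = 0.589

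That is 4.5 to 58.9 points. With identical counts of 9, 15 or 17 out of 17, the Newcombe interval is still ±30, ±24 or ±18 points.

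This interval excludes 0 while Fisher's p is 0.057. Over all outcomes, that disagreement occurs in 24 of 324 (17 per arm) and 26 of 361 (18 per arm), and never in reverse. The conditional odds-ratio interval disagrees with Fisher's test in none of them. For this table the sample odds ratio is (15×8)/(2×9) = 6.67, and the central conditional interval is 0.96 to 73.7. The agreement was checked for equal arms only.

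**Chance of p≥0.05 under assumed patient-level rates, 17 per arm.** Exact Fisher power is 0.142 at 60% v 80%, 0.561 at 40% v 80% and 0.827 at 40% v 90%. Non-significance then occurs in 86%, 44% and 17% of trials.

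**Effect of the unit on the endpoint (assumed).** Use a beta-binomial with tooth-level CRC rate p=0.80, m=2 to 4 teeth and correlation ρ=0.2 to 0.6.

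- All teeth covered: lowest at m=4, ρ=0.2, where (3.2·4.2·5.2·6.2)/(4·5·6·7) = 0.516; highest at m=2, ρ=0.6, where 0.64 + 0.6×0.16 = 0.736.
- At least one covered: lowest at m=2, ρ=0.6, where 1 − (0.04 + 0.6×0.16) = 0.864; highest at m=4, ρ=0.2, where 1 − (0.8·1.8·2.8·3.8)/840 = 0.982.

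One tooth-level rate therefore corresponds to 52% to 74% of patients, or to 86% to 98%, depending on the classification.

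**Effect of the unit on the test (assumed).** The design effect 1+(m−1)ρ runs from 1.2 to 2.8. Fisher's test on teeth with 17 patients per arm, the same m and ρ, and a common tooth-level rate of 0.5, 0.7 or 0.85 was evaluated by exact convolution. The type I error runs from 3.5% (m=2, ρ=0.2, rate 0.85) to 20.9% (m=4, ρ=0.6, rate 0.7). With two teeth and low correlation, the discreteness of Fisher's test offsets the clustering. With three or four teeth it does not: the error is 5.7% or more in every combination tried.

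**The case against.** The strongest reply is that the hypothesis wording is only loose drafting. Section 8.3 fixes the test and the threshold, so restating the null changes no p-value and no decision. That is right, and rewording alone would be editorial.

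A second reply is that the plan contains more than Fisher's test: descriptive statistics, a mixed model meant to separate patient from tooth variation, and permutation p-values. This also stands as a description. None of them, however, is linked to a CRC estimate or interval, and they are not reconciled with Fisher's test. At patient level, Fisher's test already is the permutation test of treatment labels with fixed arm sizes, so the two sentences agree there. At tooth level they agree only if teeth are permuted, which is the reading that ignores clustering. The CONSORT reporting commitment in Section 6 does not fix the estimate either, since its content is not set out in the documents.

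Two stronger readings are tempting. A reader might infer that the sponsor will declare the techniques equivalent when p≥0.05, but no section says so; the plan is silent. A reader might also infer that teeth will be analysed as independent. The text permits that but does not state it, and the mixed model shows awareness of the structure. The type I error range is therefore conditional on one reading.

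On the objectives, the design is labelled comparative and randomised, the tested hypothesis is between arms, and pain VAS is compared between groups. The mismatch there is one of wording.

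**Conclusion.** The concern holds in this form: the primary CRC comparison lacks a parameter in its null hypothesis, a unit of analysis, and an effect estimate with an interval. A patient-level gap of up to 6 patients (33 to 35 points) can be non-significant; that figure needs no assumed rate, only two-sided testing and 17 or 18 evaluable patients per arm. The 3% to 21% type I error applies only if Fisher's test is run on teeth, and it rests on assumed tooth counts, correlations and CRC rates. The shares of trials with p≥0.05 also rest on assumed rates. This should be corrected before outcomes are seen. It does not show that the plan intends a false claim of similarity.

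**What to change.** 1. **Section 8.2 and Synopsis.** State the null as equal probability, in the two arms, that a patient has CRC at 12 months, with a two-sided alternative at 0.05. Define how CRC over several teeth is classified per patient, for example every treated recession completely covered. This is an endpoint decision for the sponsor, to be made before outcomes are seen.
2. **Section 8.3, primary.** Keep Fisher's test, at patient level. Report a between-arm CRC effect measure with a 95% CI. The method is the sponsor's choice: for example the conditional odds-ratio interval, which agrees with Fisher's test in the outcomes checked, or a risk difference with a stated rule that Fisher's test decides significance.
3. **Section 8.3, tooth level.** Analyse tooth-level CRC only with a method that respects clustering: the planned mixed model with a logit link and a patient random effect, or a permutation test that permutes patients. Do not apply Fisher's test to teeth.
4. **Reading rule.** State that p≥0.05 is not evidence of similarity, because no equivalence margin is set.
5. **Minor, wording only (Sections 1 and 4).** Make the objective the randomised between-arm comparison. Replace preference by between-arm differences in pain VAS and in patient-rated aesthetics, and name the scale for the latter, since Section 4.2 gives none.

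Allocation, visits and measurements are unchanged. The costs are that the sponsor must commit to one definition of CRC per patient, which can shift the expected rate substantially, must restrict how tooth-level CRC is tested, and gives up any no-difference reading of a non-significant result. If a risk difference is chosen, its interval will occasionally exclude 0 when Fisher's test is non-significant, and that must be reported as it stands.

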8.3. Statistical Methods

Statistical analysis will be performed using commercially available software (STATA) or R environment (www.r-project.org). Both patient- and tooth-level analysis will be performed for each parameter. Therefore, mean values and standard deviations (SD), as well other descriptive statistics, for the clinical variables will be calculated for each patient per treatment.

A mixed model will be built to take into account the variability due to patient and tooth factors differentially.

Accordingly, the significance of the difference within each group and between groups before and after treatment will be evaluated with the paired samples t-test or two independent samples t-test, as appropriated, regarding all numerical data (REC, KTW, GT, PPD, percentage of root coverage and VAS scale).

Fisher's exact test will be applied for categorical data (frequency of complete root coverage).

P-values will be computed by means of permutation methods to avoid any distributional assumptions or asymptotical approximation. Differences will be considered statistically significant when the p-value was <0.05 .

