1. SYNOPSIS

TITLE	Treatment of multiple gingival recession defects with a coronally advanced flap or a modified tunnel technique and a volume stable three-dimensional xenogenic collagen matrix: a monocentric randomized clinical trial.
TRIAL LOCATION	PI: [name] [name] Dipartimento di Odontoiatria – Ospedale San Raffaele Direttore: [name] [name]
STUDY OBJECTIVES	To compare the outcomes of two muco-gingival surgery techniques, the modified coronally advanced flap (MCAF) for multiple recession defects (Zucchelli & [name] 2000) and the modified coronally advanced tunnel technique (MCAT) (Aroca 2013), performed in the Department of Periodontology of San Raffaele Hospital with the results reported in the literature. Secondarily, the study will evaluate whether patients report a preference in terms of discomfort and perception of aesthetics between the two surgical techniques.
STUDY DESIGN	Single center, National study, Comparative, Randomized, Open label
STUDY POPULATION	Main selection criteria: patients requiring root coverage procedures from the Dental Clinic of San Raffaele Vita-Salute University will be enrolled in the study. Inclusion criteria: multiple (i.e., at least 2) Miller Class I and/or II gingival recessions located in the maxillae, good general health, healthy periodontal conditions (FMPS and FMBS <25%). Exclusion criteria: smoking >10 cigarettes/day, nursing and pregnant female, contraindication against oral surgical interventions and against use of Fibro-Gide Total expected number of patients: 36 (18 for each group)
STUDY PROCEDURES	Recessions will be randomly treated by means of MCAF + CM or MCAT technique + CM. The following measurements will be recorded at baseline (prior to surgery), at 90, 180 and 360 days: Gingival recession depth (REC in mm), Keratinized tissue width (KTW in mm), Gingival thickness (GT in mm), Pocket probing depth (PPD in mm), BoP (Bleeding on Probing, PI (Plaque Index).
STUDY DEVICE	Fibro-Gide

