4.1. Primary outcome

- percentage (%) of complete root coverage (CRC) at 12 months

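### Section 8.3 leaves the unit of the CRC test open: it fits a valid per-patient analysis, but also a Fisher or permutation test on pooled teeth that ignores clustering

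*Combined protocol and SAP*

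**What the plan says.** - **Outcome.** Section 4.1 defines the primary outcome as "percentage (%) of complete root coverage (CRC) at 12 months", without saying whether the percentage is of patients or of teeth. The null hypothesis in 8.2 treats CRC as a clinical parameter: "No statistically significant differences are observed with respect to the clinical parameters CRC, at 12 months between the two treatment modalities".
- **Levels.** Section 8.3: "Both patient- and tooth-level analysis will be performed for each parameter". Neither level is called primary.
- **Test for CRC.** Only Fisher's is named: "exact test will be applied for categorical data (frequency of complete root coverage").
- **Mixed model.** "A mixed model will be built to take into account the variability due to patient and tooth factors differentially". No outcome, link function, tested effect or priority is given.
- **Permutation.** "P-values will be computed by means of permutation methods to avoid any distributional assumptions or asymptotical approximation". The unit to be permuted is not stated.
- **Synopsis.** The statistical entry that opens "Primary method of analysis: the significance of the difference within each group and between groups before and after treatment will be evaluated" repeats the t-tests and Fisher's test, but not the mixed model, the permutation or the two levels.
- **Allocation.** Section 5.1 assigns treatment to each patient by sealed envelope. The synopsis says "Recessions will be randomly treated by means of MCAF + CM or MCAT technique + CM". Section 6.1 requires at least two recessions per patient and sets no maximum.

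**The concern.** The randomised unit is the patient, and every patient contributes two or more teeth. Teeth in one mouth share the surgeon, the flap, healing and oral hygiene, so their CRC results are likely to be correlated. Fisher's test on pooled teeth counts them as independent and so overstates the information.

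Taken together, the sentences in 8.3 place a tooth-level analysis of CRC within the plan and offer Fisher's test as the only named tool for it. If that p-value carried the primary conclusion, the false positive rate could exceed the 5% the plan sets. Because the levels are unranked, a reader could not tell which of two CRC results was confirmatory. That is a weakness of pre-specification; its numerical harm is the same inflation, not a further one.

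**Working it through.** **The plan's own figure.** Section 8.1 gives a difference of 10, SD 10, alpha 0.05 and power 80%. Two-sided testing is assumed. The normal formula 2(1.96 + 0.84)² × (10/10)² gives 15.7, so 16 per arm; the t-test calculation gives 16.71, so 17. The stated 17 per arm reproduces (power 80.7%). It is sized on mean root coverage with the patient as unit, and contains no ICC.

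**Inputs for the clustering check.** From the plan: 17 patients per arm, significance at p < 0.05, at least 2 teeth per patient. Assumed: m = 2, 3 or 4 teeth for every patient; ICC ρ = 0 to 0.5; the same CRC rate π in both arms, 50% to 85%.

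**Method (exact, no simulation).** The number of covered teeth per patient is beta-binomial with size m and parameters π(1−ρ)/ρ and (1−π)(1−ρ)/ρ. The arm total is the convolution of 17 such counts. The type I error is the sum of P(T₁=a)·P(T₂=b) over all tables whose two-sided Fisher p-value, with 17m teeth per arm, is below 0.05.

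Type I error of Fisher's test on pooled teeth, π = 70%:

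| Teeth per patient | ICC 0 | ICC 0.1 | ICC 0.3 | ICC 0.5 |
|---|---|---|---|---|
| 2 | 2.67% | 3.49% | 5.32% | 7.29% |
| 3 | 3.13% | 4.95% | 9.01% | 13.12% |
| 4 | 3.33% | 6.24% | 12.47% | 18.25% |

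Other CRC rates, range over ICC 0.1 to 0.5 for 2, 3 and 4 teeth:
- π = 50%: 3.4-7.3%, 5.7-14.2%, 6.0-17.8%.
- π = 85%: 2.7-5.9%, 4.0-11.5%, 5.6-17.3%.

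With 18 per arm and π = 70%, the values at ICC 0.1/0.3/0.5 are 3.59/5.39/7.34%, 4.86/8.88/12.93% and 6.15/12.29/18.06%.

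**Where 5% is crossed.** Over π = 50-85% the break-even ICC is about 0.22-0.39 (2 teeth), 0.07-0.16 (3) and 0.06-0.08 (4). With 2 teeth and ICC 0.3 the error is 4.2-5.7% over that range: Fisher's conservatism absorbs most of the clustering.

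**Why.** The design effect is 1 + (m−1)ρ. At ρ = 0.3, 3 teeth give 1 + 2 × 0.3 = 1.6, so 51 teeth per arm count as 51/1.6 ≈ 32. Four teeth give 1.9, so 68 count as 68/1.9 ≈ 36.

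**Does permutation help?** Only if whole patients are permuted. Permuting labels over teeth gives the same p-value as Fisher's test in all 1,225, 2,704 and 4,761 possible tables (2, 3 and 4 teeth, 17 per arm). Permuting per-patient proportions over patients gives a simulated error of 2.6-4.0% at π = 70%.

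**Fisher on one yes/no result per patient** (all treated teeth covered), exact: 2.0-2.4% at π = 70%; 0.8-2.0% at π = 50% with 4 teeth and ICC 0.1-0.5.

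**The case against.** The best defence is that 8.3 reads in sequence: two levels, descriptive summaries per patient, a mixed model for patient and tooth variability, then the simple tests. On that reading the mixed model carries the teeth and the simple tests use per-patient data. Allocation and sample size are also per patient. Permuting whole patients is fully compatible with the text and would make even a tooth-level statistic valid. The synopsis can be read as an abbreviation.

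Most of this stands. The authors plainly recognised clustering, and no sentence prescribes Fisher's test on pooled teeth. A reader might infer that the plan is wrong as written, or that its primary test will run at 12-18% error. The documents support neither: the pooled-tooth test follows only by implication, and the high figures need 4 teeth with ICC 0.3-0.5, or 3 teeth with ICC near 0.5. Nor does the synopsis wording show that recessions are randomised individually; 5.1 settles that.

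What does not stand is that the text closes the gap. The mixed model is tied to no outcome and is absent from the synopsis, the permuted unit is unnamed, and a patient-level CRC is nowhere defined.

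**Conclusion.** The point holds as an ambiguity with a measurable cost on one branch, and should be fixed as a cheap improvement. Section 8.3 admits a valid analysis and an invalid one for the primary outcome, and nothing in the plan chooses between them. On the invalid branch the exact type I error at CRC 70% is 3.5-7.3%, 5.0-13.1% and 6.2-18.3% for 2, 3 and 4 teeth over ICC 0.1-0.5. These figures rest on an equal number of teeth per patient, a beta-binomial model, and assumed ICC and CRC rates. They apply only if teeth are pooled or permuted singly and that result is used for the primary conclusion. With two teeth per patient, the minimum the plan allows, the inflation is immaterial up to an ICC of about 0.3.

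**What to change.** In 8.3 and in the synopsis entry on the primary method of analysis:

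1. Add:
> All permutation p-values permute treatment labels among patients, with all teeth of a patient moving together. Fisher's exact test is applied only to one result per patient and not to pooled teeth. Tooth-level CRC is analysed by a logistic mixed model with a random patient intercept, as supportive.

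2. Name one primary patient-level CRC analysis. The choice of estimand is the sponsor's:
   - the mean per-patient proportion of teeth with CRC, tested by patient-level permutation; or
   - a yes/no result per patient (all treated teeth covered), tested by two-sided Fisher's exact test.

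   In either case the confidence interval should invert the same test. For Fisher's test, the interval built from two one-sided 2.5% limits disagrees with the p-value in 16 of 342 tables at 18 v 17 patients.

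3. Align the synopsis sentence on random treatment of recessions with the per-patient allocation in 5.1.

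**Cost.** No new data or software, but step 2 is a decision on the estimand, not just wording. The tooth-level p-value will usually be less favourable than a pooled one. Both patient-level tests are conservative. The yes/no result loses power: for CRC 85% v 60% with 3 teeth and ICC 0.1/0.3/0.5 it has 52/46/38%, against 66/54/45% for permutation of proportions. For an illustrative 80% v 70% (2-4 teeth, ICC 0.1-0.5) it has only about 6-10%. The supportive mixed model is slightly liberal at this size (simulated error 4.9-6.7%).

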4.2. Secondary outcomes

- percentage of root coverage (RC %) at 3, 6 and 12 months
- keratinized tissue width (KTW) at 3, 6 and 12 months
- gingival thickness (GT) at 3, 6 and 12 months
- post-surgical pain (PP),
- amount of drug intake after surgery
- patient perception of aesthetics at 6 and 12 months
- color match (blending), contour (correct outline of the gingival margin at adjacent teeth), contiguity (evaluated based on the visible confluence between the treated area and the adjacent soft tissues), degree of keloid formation scored at the 1-year post-surgical evaluation will be measured by an expert periodontist.
- duration of surgery (from anesthesia to last suture).

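### Gingival thickness and keratinised tissue width are compared between arms without adjustment for the baseline values already collected, which may cost precision

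*Combined protocol and SAP*

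**What the plan says.** Section 4.2 lists "keratinized tissue width (KTW) at 3, 6 and 12 months" and "gingival thickness (GT) at 3, 6 and 12 months" among the secondary outcomes. Both have a pre-surgical value in every patient: the Synopsis (Study procedures) states "The following measurements will be recorded at baseline (prior to surgery), at 90, 180 and 360 days", and the Flow-chart places them in the screening column.

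For the analysis, section 8.3 says that differences "will be evaluated with the paired samples t-test or two independent samples t-test, as appropriated, regarding all numerical data". The list that follows includes recession depth (REC), KTW, GT and probing depth (PPD). No covariate is named.

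The same section adds "Both patient- and tooth-level analysis will be performed for each parameter" and "A mixed model will be built to take into account the variability due to patient and tooth factors differentially". It gives no fixed effects and no baseline term for that model, and does not say whether the model or the t-tests decide the comparison. It also states "P-values will be computed by means of permutation methods".

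The Synopsis (Statistical considerations) opens with "Primary method of analysis: the significance of the difference within each group and between groups before and after treatment will be evaluated", goes on to the t-tests, and does not mention the mixed model.

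**The concern.** An independent-samples t-test cannot use the baseline value as a covariate. The wording on differences between groups before and after treatment allows two readings, and only one can apply. If final values are compared, baseline is ignored. If changes from baseline are compared, baseline is used but its slope is fixed at 1, which is usually too steep. Analysis of covariance (ANCOVA) estimates the slope from the data.

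The trial is small and was sized on mean root coverage, so KTW and GT have no precision to spare. If baseline is moderately prognostic, the plan discards information that the screening visit already supplies. The plan also leaves three candidate analyses open for the same outcome (final value, change, and a mixed model still to be built), so the choice could be made after the data are seen.

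Bias is not at issue. Complete root coverage (Fisher's exact test), post-surgical pain and the sample size are untouched.

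**Working it through.** **The plan's own figure.** Section 8.1 uses a 10-point difference in mean root coverage, SD 10, alpha 0.05 and power 80%. Two-sided testing is assumed, since one-sided testing gives 13 per arm.

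n = 2 × (1.96 + 0.842)² × (10/10)² = 15.7, so 16 per arm by the normal approximation. The noncentral t gives 17 (power 0.781 at 16 and 0.807 at 17). The stated 17 is therefore reproduced, but for mean root coverage. For KTW or GT, a final-value t-test with 17 per arm has 80% power only for a difference of about 0.99 SD.

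**Inputs for the comparison**
- n = 18 per arm: 17 plus 1 for dropout (section 8.1).
- r, the correlation of baseline and follow-up patient means: not in the documents, assumed 0 to 0.7. The entry requirement of 1 mm or more of keratinised tissue (section 6.1) cuts off the lower end of baseline KTW and may lower r.
- k, baseline SD divided by follow-up SD: not in the documents, assumed 1, with 0.8 and 1.25 as alternatives.

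**Formulas**, with variance of the arm difference relative to a final-value t-test:
- final value: 1
- change score: 1 + k² − 2rk
- ANCOVA: (1 − r²) × [1 + 1/(2n − 4)]. At n = 18 the bracket is 1 + 1/32 = 1.031, the cost of estimating one slope.

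The 95% confidence interval half-width is 2.032 × √(2/18) = 0.677 SD for the final-value test. For ANCOVA it is 2.035 × √((2/18) × ratio). At r = 0.5, for example, the ratio is 1.031 × 0.75 = 0.773 and the half-width is 2.035 × √(0.1111 × 0.773) = 0.596 SD.

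| r | ANCOVA ÷ final value | ANCOVA half-width (SD) | ANCOVA ÷ change score, k = 1 |
|---|---|---|---|
| 0 | 1.031 | 0.689 | 0.516 |
| 0.2 | 0.990 | 0.675 | 0.619 |
| 0.3 | 0.938 | 0.657 | 0.670 |
| 0.5 | 0.773 | 0.596 | 0.773 |
| 0.7 | 0.526 | 0.492 | 0.877 |

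- *Break-even against final values:* r = √(1 − 1/1.03125) = 0.174.
- *Break-even against change scores, k = 1:* r = 2/1.03125 − 1 = 0.939.
- *Other SD ratios, against change scores:* for r = 0 to 0.7, the ratio runs from 0.629 to 1.011 at k = 0.8, and from 0.402 to 0.647 at k = 1.25.
- *Equivalent sample size against final values:* 18/0.773 ≈ 23 per arm at r = 0.5, and 18/0.526 ≈ 34 at r = 0.7.

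**Does the mixed model recover this?** Trials of 36 patients were simulated, assuming 2 to 5 teeth each and within-patient correlation 0.5, with 3,000 trials per scenario. Variances are relative to the patient-mean final-value difference.

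| r | Mixed model, no baseline term | Mixed model, patient-mean baseline plus tooth deviation | Patient-mean ANCOVA |
|---|---|---|---|
| 0.3 | 0.990 | 0.933 | 0.941 |
| 0.5 | 0.993 | 0.771 | 0.774 |
| 0.7 | 0.998 | 0.520 | 0.525 |

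A random patient effect alone gains almost nothing; the baseline term is what helps. A second simulation of patient-mean ANCOVA gave 0.93, 0.81 and 0.53. If the between-patient correlation is 0.2 and the within-patient correlation 0.7, a single tooth-level slope gives 0.992, against 0.917 with the two-part baseline.

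**REC.** Mean coverage of 85–95% is taken from section 8.1. Coverage SD of 10–15 points capped at 100%, and baseline depth of 2.5–3 mm with SD 0.5–0.8 mm, are assumed. Simulated r is then 0.14 to 0.44 and the ANCOVA ratio to final values is 0.836 to 1.012, so the gain is small.

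**Permutation p-values.** The ANCOVA t statistic was referred to permutations of arm labels across patients, on skewed data rounded to 0.5 mm with baseline cut off at 1 mm (4,000 trials, 999 permutations). Type I error was 5.0% (SE 0.3).

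**The case against.** The strongest reply is that nothing here is invalid. The t-tests are sound under randomisation, the outcomes are secondary, and the gain rests on a correlation that the documents do not give. Against final values, adjustment gains almost nothing at r = 0.2 to 0.3 and loses slightly below r = 0.17. This stands, and it limits the point to a recommendation.

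The plan may also already use baseline: a change-score comparison is a natural reading, and the mixed model could include baseline when it is built. Neither is a commitment. On the change-score reading ANCOVA usually does better, although with k = 0.8 and r = 0.7 it is 1% worse, so the break-even of 0.94 holds only for equal SDs. A Synopsis that omits the mixed model may simply be shorter, but it does name the t-tests as the primary method.

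Some objections concern scope. No gain was calculated for PPD, whose range is restricted by section 6.1, and the gain for REC is small. The case for splitting the baseline at tooth level rests on one constructed scenario. Leaving percentage root coverage unadjusted, because it is already relative to baseline recession, is a judgement and was not calculated. These objections are fair; the point does not depend on any of those items.

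Lastly, section 8.1 plans on 17 evaluable patients per arm. The slope cost is then 1 + 1/30 = 1.033, the ratio at r = 0.5 is 0.775, and the final-value half-width is 2.037 × √(2/17) = 0.70 SD. The conclusion is the same.

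**Conclusion.** The concern holds, as a matter of precision in two listed secondary outcomes. The plan commits to no baseline adjustment for KTW or GT, although it collects the baseline values. Over r = 0 to 0.7 at 18 per arm, the worst result of adjusting is about 3% more variance. The best is 47% less against a final-value test and, with equal SDs, 48% less against a change-score test (60% less if the baseline SD is 1.25 times the follow-up SD). The actual gain cannot be fixed from the documents; it depends on r and on the SD ratio, both assumed here. It is a change the plan should make, but the trial's validity does not hang on it.

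**What to change.** In section 8.3 and in the Synopsis:

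- Make the between-arm analysis of KTW and GT at 3, 6 and 12 months an ANCOVA on patient means, with arm and the patient-mean baseline of the same variable as terms.
- Take p-values from permuting arm labels across patients, in line with the permutation methods already planned.
- State that this model, and not the t-test, decides the arm comparison for these outcomes, and treat the within-arm paired tests as descriptive.
- For the tooth-level analysis, specify the mixed model: arm, patient-mean baseline and each tooth's deviation from it as fixed effects, and patient as a random effect.
- REC and PPD may use the same ANCOVA as supportive measures. Percentage root coverage, the pain scale and Fisher's test for complete root coverage can stay as they are.

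The first three items are the core; the last two are refinements. The cost is wording only: no new data, visits or patients. The ANCOVA uses one degree of freedom and the mixed model two. If baseline proves not to be prognostic, the ANCOVA half-width is 0.69 SD instead of 0.68 SD.
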